#### **10.3.3 Expedited Reporting Guidelines**

Use the NCI protocol number and the protocol-specific patient ID assigned during trial registration on all reports.

**Note: A death on study requires both routine and expedited reporting, regardless of causality as long as the death occurred within 30 days after the last administration of the investigational agent. Attribution to treatment or other cause must be provided.**

Death due to progressive disease should be reported as **Grade 5 “Disease progression”** in the system organ class (SOC) “General disorders and administration site conditions.” Evidence that the death was a manifestation of underlying disease (e.g., radiological changes suggesting tumor growth or progression: clinical deterioration associated with a disease process) should be submitted.

**Late Phase 2 and Phase 3 Studies: Expedited Reporting Requirements for Adverse Events that Occur on Studies under an IND/IDE within 30 Days of the Last Administration of the Investigational Agent/Intervention**

**FDA REPORTING REQUIREMENTS FOR SERIOUS ADVERSE EVENTS (21 CFR Part 312)**

**NOTE:** Investigators **MUST** immediately report to the sponsor (NCI) **ANY** Serious Adverse Events, whether or not they are considered related to the investigational agent(s)/intervention (21 CFR 312.64)

An adverse event is considered serious if it results in **ANY** of the following outcomes:

- 1) Death
- 2) A life-threatening adverse event
- 3) An adverse event that results in inpatient hospitalization or prolongation of existing hospitalization for  $\geq 24$  hours
- 4) A persistent or significant incapacity or substantial disruption of the ability to conduct normal life functions
- 5) A congenital anomaly/birth defect.
- 6) Important Medical Events (IME) that may not result in death, be life threatening, or require hospitalization may be considered serious when, based upon medical judgment, they may jeopardize the patient or subject and may require medical or surgical intervention to prevent one of the outcomes listed in this definition. (FDA, 21 CFR 312.32; ICH E2A and ICH E6).

**ALL SERIOUS** adverse events that meet the above criteria **MUST** be immediately reported to the NCI via electronic submission within the timeframes detailed in the table below.

| Hospitalization                                | Grade 1 Timeframes | Grade 2 Timeframes | Grade 3 Timeframes | Grade 4 & 5 Timeframes  |
|--|--------------------|--------------------|--------------------|-------------------------|
| Resulting in Hospitalization $\geq 24$ hrs     |                    | 10 Calendar Days   |                    | 24-Hour 5 Calendar Days |
| Not resulting in Hospitalization $\geq 24$ hrs | Not required       |                    | 10 Calendar Days   |                         |

**NOTE:** Protocol specific exceptions to expedited reporting of serious adverse events are found in the Specific Protocol Exceptions to Expedited Reporting (SPEER) portion of the CAEPR

**Expedited AE reporting timelines are defined as:**

- “24-Hour; 5 Calendar Days” - The AE must initially be submitted electronically within 24 hours of learning of the AE, followed by a complete expedited report within 5 calendar days of the initial 24-hour report.
- “10 Calendar Days” - A complete expedited report on the AE must be submitted electronically within 10 calendar days of learning of the AE.

Serious adverse events that occur more than 30 days after the last administration of investigational agent/intervention and have an attribution of possible, probable, or definite require reporting as follows:

**Expedited 24-hour notification followed by complete report within 5 calendar days for:**

- All Grade 4, and Grade 5 AEs

**Expedited 10 calendar day reports for:**

- Grade 2 adverse events resulting in hospitalization or prolongation of hospitalization
- Grade 3 adverse events

For studies using PET or SPECT IND agents, the AE reporting period is limited to 10 radioactive half-lives, rounded UP to the nearest whole day, after the agent/intervention was last administered. Footnote “1” above applies after this reporting period.

Effective Date: May 5, 2011

#### 10.3.4 Adverse Events of Special Interest

Adverse Event Special Interest (AESIs) are a subset of events of scientific and/or medical concern specific to this protocol, for which ongoing monitoring and communication by the Investigator to the Sponsor is required.

*General AESI:*

- Cases of potential drug-induced liver injury that include an elevated ALT or AST in combination with either an elevated bilirubin or clinical jaundice, as defined by Hy's Law and based on the following observations: - Treatment-emergent ALT or AST  $> 3 \times$  baseline value in combination with total bilirubin  $> 2 \times$  ULN (of which  $> 35\%$  is direct bilirubin) - Treatment-emergent ALT or AST  $> 3 \times$  baseline value in combination with clinical jaundice

Suspected transmission of an infectious agent by the study treatment, as defined below - Any organism, virus, or infectious particle (e.g., prion protein transmitting transmissible spongiform encephalopathy), pathogenic or non-pathogenic, is considered an infectious agent. A transmission of an infectious agent may be suspected from clinical symptoms or laboratory findings that indicate an infection in a patient exposed to a medicinal product. This term applies only when a contamination of study treatment is suspected.

*Atezolizumab:*

AESI for Atezolizumab are:

- Systemic lupus erythematosus
- Events suggestive of hypersensitivity, infusion-related reactions, cytokine-release syndrome, macrophage activating syndrome, hemophagocytic lymphohistiocytosis
- Nephritis
- Ocular toxicities (e.g., uveitis, retinitis, optic neuritis)
- Grade  $\geq 2$  cardiac disorders (e.g., atrial fibrillation, myocarditis, pericarditis)
- Vasculitis
- Autoimmune hemolytic anemia
- Severe cutaneous reactions (e.g., Stevens-Johnson syndrome, dermatitis bullous, toxic epidermal necrolysis)

*Cobimetinib:*

- AESI for Cobimetinib are:
- Any grade Serous retinopathy, including events of retinal detachment, retinal pigment epithelium detachment, neurosensory retinal detachment or central serous chorioretinopathy
- Significant liver toxicity: AST and/or ALT  $> 10 \times$  upper limit of normal
- Symptomatic heart failure / Grade  $\geq 2$  left ventricular dysfunction
- Grade  $\geq 3$  CPK elevation or Rhabdomyolysis
- Grade  $\geq 3$  Diarrhea
- Grade  $\geq 3$  rash

*Biopsy:*

Adverse Events of Special Interest (AESIs) for this study are related to the biopsy component of the study. These events should be captured in Rave as they occur and should be reported expeditiously according to the table above. Four of these AESIs are not currently part of the CTCAE and must be reported in Rave/CTEP-AERS using the term: Injury, poisoning and

procedural complications - Other, specify. The AESI Terms and Grading Table below (Section 10.3.4.1) lists the AESI terms and their grading. The AESI Reporting Table (Section 10.3.4.2) provides instruction on how to record these events in Rave/CTEP-AERS.

### 10.3.4.1 Adverse Event Special Interest (AESI) Terms and Grading

#### Adverse Event Special Interest (AESI) Terms and Grading

| AESI  | Grade 1  | Grade 2  | Grade 3  | Grade 4  | Grade 5 | Definition  |
|---|--|--|--|--|---------|---|
| Biopsy-related hemorrhage                                      | Symptomatic hematoma requiring medications   | Any hematoma (symptomatic or asymptomatic) requiring unplanned observation with less than 24 hours of hospitalization  | Hemorrhage requiring transfusion, radiologic, endoscopic or surgical intervention or greater than 24 hours of hospitalization                            | Hemorrhage with life-threatening consequences; urgent intervention indicated         | Death   | A disorder characterized by bleeding related to a biopsy procedure.   |
| Biopsy-related nerve injury                                    | Symptomatic nerve pain or injury requiring medications                             | Any nerve injury requiring unplanned observation with less than 24 hours of hospitalization  | Any nerve injury requiring surgical intervention or greater than 24 hours of hospitalization   | Nerve injury with life-threatening consequences; urgent intervention indicated       | Death   | A finding of damage to a nerve related to a biopsy procedure.   |
| Biopsy-related organ injury                                    | Symptomatic organ pain or injury requiring medications                             | Any organ injury requiring unplanned observation with less than 24 hours of hospitalization  | Any organ injury that requires radiologic, endoscopic or surgical intervention or greater than 24 hours of hospitalization                               | Organ injury with life-threatening consequences; urgent intervention indicated       | Death   | A finding of damage to an organ related to a biopsy procedure.  |
| Biopsy-related anesthesia (local or moderate sedation) effects | Symptomatic anesthesia effects requiring medications                               | Any biopsy-related anesthesia effects requiring medical intervention for reversal of symptomatic effects and/or requiring unplanned observation with less than 24 hours of hospitalization | Any anesthesia effects requiring intervention for reversal or treatment of symptomatic effects and/or requiring greater than 24 hours of hospitalization | Anesthesia effects with life-threatening consequences; urgent intervention indicated | Death   | A disorder characterized by reactions related to the administration of local or moderate sedation given for a biopsy procedure. |
| Pneumothorax   | Asymptomatic; clinical or diagnostic observations only; intervention not indicated | Symptomatic; intervention indicated  | Sclerotherapy and/or operative intervention indicated; hospitalization indicated   | Life-threatening consequences; urgent intervention indicated                         | Death   | A disorder characterized by abnormal presence of air in the pleural cavity resulting in the collapse of the lung.               |
| Pain   | Mild pain  | Moderate pain; limiting instrumental ADL   | Severe pain; limiting self care ADL  | -  | -       | A disorder characterized by the sensation of marked discomfort, distress or agony.  |
| Wound infection  | Localized, local intervention indicated  | Oral intervention indicated (e.g., antibiotic, antifungal, or antiviral)   | IV antibiotic, antifungal, or antiviral intervention indicated; invasive intervention indicated  | Life-threatening consequences; urgent intervention indicated                         | Death   | A disorder characterized by an infectious process involving the wound.  |
| Allergic reaction  | Systemic intervention not indicated  | Oral intervention indicated  | Bronchospasm; hospitalization indicated for clinical sequelae; intravenous intervention indicated  | Life-threatening consequences; urgent intervention indicated                         | Death   | A disorder characterized by an adverse local or general response from exposure to an allergen.                                  |

10.3.4.2 Adverse Event Special Interest (AESI) Reporting

**Adverse Event Special Interest (AESI) Reporting**

| AESI Term  | CTCAE term to Select  | Other, specify language to record:                             |
|--|---|--|
| Pneumothorax*  | Pneumothorax  | N/A  |
| Pain*  | Pain  | N/A  |
| Wound infection*   | Wound infection   | N/A  |
| Allergic reaction*   | Allergic reaction   | N/A  |
| Biopsy-related hemorrhage**                                      | Injury, poisoning and procedural complications - Other, specify | Biopsy-related hemorrhage                                      |
| Biopsy-related nerve injury**                                    | Injury, poisoning and procedural complications - Other, specify | Biopsy-related nerve injury                                    |
| Biopsy-related organ injury**                                    | Injury, poisoning and procedural complications - Other, specify | Biopsy-related organ injury                                    |
| Biopsy-related anesthesia (local or moderate sedation) effects** | Injury, poisoning and procedural complications - Other, specify | Biopsy-related anesthesia (local or moderate sedation) effects |

\*Select the indicated current CTCAE Term.

\*\*Select CTCAE term, “Injury, poisoning and procedural complications - Other, specify” and fill in the ‘Specify’ with the AESI term when prompted in Rave.

For example, if the subject experienced a biopsy-related hemorrhage, select Injury, poisoning and procedural complications - Other, specify and write in ‘Biopsy-related hemorrhage’ when prompted in Rave and/or CTEP-AERS.

## 10.4 Routine Adverse Event Reporting

All Adverse Events **must** be reported in routine study data submissions. **AEs reported expeditiously through CTEP-AERS must also be reported in routine study data submissions.**

Adverse event data collection and reporting, which are required as part of every clinical trial, are done to ensure the safety of patients enrolled in the studies as well as those who will enroll in future studies using similar agents. AEs are reported in a routine manner at scheduled times during the trial using Medidata Rave. For this trial the Adverse Event CRF is used for routine AE reporting in Rave.

## 10.5 Pregnancy

Although not an adverse event in and of itself, pregnancy as well as its outcome must be documented via **CTEP-AERS**. In addition, the **Pregnancy Information Form** included within the NCI Guidelines for Adverse Event Reporting Requirements must be completed and submitted to CTEP. Any pregnancy occurring in a patient or patient's partner from the time of consent to 90 days after the last dose of study drug must be reported and then followed for outcome. Newborn infants should be followed until 30 days old. Please see the "NCI Guidelines for Investigators: Adverse Event Reporting Requirements for DCTD (CTEP and CIP) and DCP INDs and IDEs" (at [http://ctep.cancer.gov/protocolDevelopment/adverse\\_effects.htm](http://ctep.cancer.gov/protocolDevelopment/adverse_effects.htm)) for more details on how to report pregnancy and its outcome to CTEP.

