- 3.1.9 Patients must be willing to undergo 2 sets of core needle biopsies. If possible, biopsied sites should be different than those used for measurable disease/RECIST measurements, but this is not mandatory.
- 3.1.10 Patients must have an estimated life expectancy of greater than 3 months.
- 3.1.11 Patients must be able to swallow pills
- 3.1.12 Patients should not have evidence of retinal pathology on ophthalmologic examination; or neurosensory retinal detachment, RVO, or neovascular macular degeneration.
- 3.1.13 The effects of atezolizumab, cobimetinib, and CDX-1127 (varlilumab) on the developing human fetus are unknown. For this reason, women of child-bearing potential and men must agree to use adequate contraception (hormonal or barrier method of birth control; abstinence) prior to study entry, for the duration of study participation, and 5 months after the last dose of Atezolizumab. Should a woman become pregnant or suspect she is pregnant while she or her partner is participating in this study, she should inform her treating physician immediately. Men treated or enrolled on this protocol must also agree to use adequate contraception prior to the study, for the duration of study participation, and 5 months (150 days) after completion of atezolizumab, cobimetinib, and CDX-1127 (varlilumab) administration.
- 3.1.14 Ability to understand and the willingness to sign a written informed consent document.

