#### 6.1.1.4 Pregnancy

All women of child bearing potential should be instructed to contact the investigator immediately if they suspect they might be pregnant (e.g., missed or late menstrual period) at any time during study participation and 5 months after the last dose of Atezolizumab or 3 months after the last dose of cobimetinib.

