#### **6.4 Duration of Therapy**

In the absence of treatment delays due to adverse event(s), treatment may continue until one of the following criteria applies:

- Disease progression
- Intercurrent illness that prevents further administration of treatment
- Unacceptable toxicity [adverse event(s)]
- Patient decides to withdraw from the study
- General or specific changes in the patient's condition render the patient unacceptable for further treatment in the judgment of the investigator
- Clinical progression
- Patient non-compliance
- Pregnancy
  - All women of child bearing potential should be instructed to contact the investigator immediately if they suspect they might be pregnant (e.g., missed or late menstrual period) at any time during study participation and 5 months after the last dose of Atezolizumab.
  - The investigator must immediately notify CTEP in the event of a confirmed pregnancy in a patient participating in the study.
- Termination of the study by sponsor
- The drug manufacturer can no longer provide the study agent

The reason(s) for protocol therapy discontinuation, the reason(s) for study removal, and the corresponding dates must be documented in the Case Report Form (CRF).

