**Patient Care Implications:**

Male patients and female patients of childbearing potential should utilize contraception and take active measures to avoid pregnancy while undergoing atezolizumab treatment and for at least 150 days after the last dose of atezolizumab or 3 months after the last dose of cobimetinib.

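### Pregnancy reporting and outcome follow-up in 10.5 stops at 90 days, up to 60 days before the protocol's own 5-month contraception window ends

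*Combined protocol and SAP*

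**What the plan says.** Section 10.5 opens by requiring pregnancies and their outcomes to be documented in CTEP-AERS and a Pregnancy Information Form to be sent to CTEP. It then sets the period: a pregnancy in a patient or partner "from the time of consent to 90 days after the last dose of study drug must be reported and then followed for outcome". Newborns are followed to 30 days of age.

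Other sections use a longer period:

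- **3.1.13** requires women of child-bearing potential and men to use contraception "for the duration of study participation, and 5 months after the last dose of Atezolizumab". A later sentence sets the men's period at "5 months (150 days) after completion of atezolizumab, cobimetinib, and CDX-1127 (varlilumab) administration".
- **8.1.1** asks male and female patients to avoid pregnancy "for at least 150 days after the last dose of atezolizumab", followed by an alternative of 3 months after cobimetinib. **8.1.3** joins the same two periods with *and*.
- **6.1.1.4** tells women to contact the investigator about a suspected pregnancy "at any time during study participation and 5 months after the last dose of Atezolizumab or 3 months after the last dose of cobimetinib". **6.4** repeats the 5-month atezolizumab period.

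Two provisions bear on who is told. Section 6.4 says: "The investigator must immediately notify CTEP in the event of a confirmed pregnancy in a patient participating in the study". Section 3.1.13 says that if a woman becomes pregnant "while she or her partner is participating in this study, she should inform her treating physician immediately".

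**The concern.** A protocol that asks patients to avoid pregnancy for 150 days treats those 150 days as the period of possible fetal risk. Pregnancies within that period are the ones whose outcomes the sponsor would want to know. Section 10.5 ends its explicit duty at day 90 and gives no reason for the earlier stop.

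The result is uneven. A woman on the trial who becomes pregnant on day 120 after atezolizumab is told to call the site, and 6.4 may send that news to CTEP, but no dated rule requires the outcome to be followed. If a male patient's partner becomes pregnant on day 120, no provision that clearly applies at that point requires a report to CTEP.

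The data are few, but each case is informative. Section 2.3.4 describes the triplet as first-in-human and 3.1.13 calls the fetal effects unknown. Section 2.2.2.2.3 reports that cobimetinib was teratogenic and embryotoxic in rats at 0.9 to 1.4 times human exposure.

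**Working it through.** **Inputs**

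- Reporting and follow-up window: 90 days from the last dose of study drug (10.5).
- Contraception window: 5 months from the last atezolizumab dose (3.1.13, 8.1.1, 8.1.3). For men it is also 150 days from completion of all three drugs (3.1.13).
- Dosing in a 28-day cycle: atezolizumab and varlilumab on Days 1 and 15, always on the same day; cobimetinib on Days 1 to 21, Arm A only (6.1, 7.1.1).

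**Step 1: the plan's own conversion.** 5 × 30 = 150 days, as 3.1.13 states.

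**Step 2: the gap.** Let L be the days from the last atezolizumab dose to the last cobimetinib dose.

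- Men, either arm, on the all-drug clock in 3.1.13: both windows start at the last dose of any drug, so the gap is 150 - 90 = **60 days**.
- Women, Arm B: both antibodies are given on the same day, so 150 - 90 = **60 days**.
- Women, Arm A: contraception ends 150 days after atezolizumab and the 10.5 window ends L + 90 days after it, so the gap is 150 - (90 + L) = 60 - L.

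For Arm A women:

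| Case | L | Gap (60 - L) |
|---|---|---|
| Scheduled: last atezolizumab Day 15, last cobimetinib Day 21 | 6 | **54 days** |
| Assumed: Day 15 infusion omitted, last atezolizumab Day 1, cobimetinib to Day 21 | 20 | 40 days |
| Assumed: cobimetinib continues 30 days after atezolizumab | 30 | 30 days |
| Assumed: cobimetinib continues 60 days or more | ≥ 60 | none |

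Check of the scheduled case: contraception ends on Day 15 + 150 = 165; the 10.5 window ends on Day 21 + 90 = 111; 165 - 111 = 54.

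**Step 3: calendar months.** Counted by calendar, 5 months is 150 to 153 days, so the 60-day figure becomes 60 to 63.

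**Step 4: what else covers the period after day 90**

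| Route | Patient pregnancy | Partner pregnancy | Outcome |
|---|---|---|---|
| 6.4, notice to CTEP | Yes, no day limit, while participating | Not mentioned | Not mentioned |
| 3.1.13, tell the physician | Yes, but no duty to inform CTEP | Yes, but no duty to inform CTEP | Not mentioned |
| 10.5, opening sentences | Undated | Undated | Undated |
| 10.3.3, late serious events | Only as a serious event, at least possibly attributed, at a listed grade | Not mentioned | A birth defect may qualify; an uneventful birth would not |

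The study calendar assesses adverse events for at least 30 days after the last dose, and 6.5 follows disease status thereafter. Neither is stated to collect pregnancies.

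**Step 5: after the change.** With 150 days from the last dose of any drug, the gap is 150 - 150 = 0 for men and for Arm B women. For Arm A women on schedule, the 10.5 window would end on Day 21 + 150 = 171, which is 6 days beyond contraception (171 - 165). The 3-month cobimetinib period falls inside it.

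**The case against.** The arithmetic is not in dispute. The best counter-argument is that 10.5 sets a minimum: its opening sentences carry no day limit and already require outcomes to be documented, and it does not say that later pregnancies may be ignored. It also refers to NCI guidelines, not available here, that may extend the duty. This stands in part. The gap is in the explicit rule, not a proven gap in practice. Still, the dated sentence is the one that says which pregnancies must be reported and followed, and a site may reasonably read it as the limit.

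Second, 6.4 is stronger than it may look. Its CTEP notice follows directly on a 5-month instruction to patients, and 6.5 keeps patients under follow-up well past day 90, so a female patient's pregnancy would probably reach CTEP. That is fair. It leaves partner pregnancies uncovered and outcome follow-up resting on the undated text.

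Third, the windows are not uniform. Sections 8.1.1 and 6.1.1.4 offer 3 months after cobimetinib as an alternative, close to 90 days, and that is the drug with stated animal evidence of fetal harm. Section 8.1.1 also counts men's contraception from atezolizumab, on which clock the scheduled Arm A male figure is 54 days, not 60. Both points are correct. But Arm B never receives cobimetinib, 8.1.3 requires both periods, and 3.1.13 counts men's 150 days from completion of all three drugs. The longer window governs.

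Finally, this is a small matter: no endpoint is touched and few cases are expected. That is true, and the recommendation is sized accordingly.

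**Conclusion.** The concern holds. The explicit rule for reporting pregnancies and following their outcome ends up to 60 days before the protocol's contraception window: 60 days for partners of male patients in both arms and for Arm B women, and 54 days for Arm A women on schedule, shrinking if cobimetinib continues longer. After day 90, partner pregnancies and the outcomes of patient pregnancies depend on how a site reads 10.5 against 6.4.

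These figures use the protocol's 150-day conversion and, for men, the all-drug clock in 3.1.13. They measure calendar time, not expected missed cases. The content of the NCI guidelines cited in 10.5 could not be checked. Sample size, power, efficacy analysis and treatment decisions are unaffected. This is an inconsistency in safety reporting that should be corrected because the correction is cheap and the fetal effects are unknown.

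**What to change.** In 10.5, replace 90 days with 5 months (150 days) after the last dose of study drug, for pregnancies in both patients and partners, and keep outcome follow-up tied to that period. Because this clock starts at the last dose of any agent, it covers every contraception and notification window in 3.1.13, 6.1.1.4, 6.4, 8.1.1 and 8.1.3 on the 150-day conversion. It runs slightly past the contraception window for Arm A women, which is harmless.

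The cost is one phrase in an amendment and a small added reporting burden for any pregnancy between days 90 and 150.
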